5.4. Interim Analysis and Data Monitoring

N/A

5.5. Multicenter Studies

This study is conducted as a multicenter clinical investigation. The data of all sites will be pooled for statistical analysis.

5.6. Multiple Comparisons/Multiplicity

No statistical tests will be performed. Only descriptive analyses including 95% confidence intervals are planned.

5.7. Examination of Subgroups

Subgroups will not be considered for analysis.

6. Study Population Characteristics

In general, statistical tables described in this chapter will show data separated by analysis population (safety set, per-protocol set) and for the total analysis population.

6.1. Population Overview

A frequency table will be prepared describing the number of patients screened, not eligible (i.e. screen failure), treated, and implanted (ARGOS-IO sensor). This table will present the frequencies by site and in total. The reason for screen failure will be shown in a patient data listing.

Furthermore, the date of the first patient in (FSI) (date of informed consent) and the date of last patient out (LSO) will be presented for the treated patients. FSI will be derived using the date of the Screening visit. LSO will be derived using the date of study termination

Inclusion and exclusion criteria will be listed per patient in a patient data listing.

The number and percentage of patients included in the SFS and PPS will be tabulated in total. Percentages are based on the number of treated patients.

A frequency table will be prepared describing for the treated patients the patient disposition at the end of the clinical investigation (categories: completed, early termination) for each analysis population. The treated patients with premature termination of the clinical investigation will be summarized by the pre-specified primary reason for premature termination. Further specifications given for the reasons of premature termination will be shown in a patient data listing.

All patient summary data will be listed.

6.2. Protocol Deviations

A frequency table will be prepared presenting the number and percentage of all treated patients with at least one deviation from the CIP.

Statistical Analysis Plan

Version 1.0 [Final], 09-Jan-2018

In addition, the number and percentage of all treated patients with deviations will be summarized by category affected. Correspondingly, the number and percentage of all treated patients with deviations will be summarized by involvement of deviation.

A patient data listing will be prepared displaying for each patient the protocol deviations.

6.3. Patients Excluded from Analysis Populations

Appendix 13.2 lists all patients excluded from any analysis population. A patient data listing will be prepared displaying excluded patients and the reason(s) for exclusion.

7. Demographics and Other Baseline Characteristics

Demographics and baseline characteristics (e.g. sex, age, educational level, disease characteristics, prior and concomitant treatments, medical history) will be evaluated for the SFS, and PPS.

7.1. Demographics

Age, weight and height at screening will be described by summary statistics. The age of the patient (in years) is exported from the database and will be used.

The distribution of the demographic characteristics sex, ethnicity and educational level will be tabulated for the pre-specified categories by frequencies and percentages.

7.2. Disease Characteristics concerning Study Eye

The number and percentage of patients will be presented by category for

- Study eye (categories: OS, OD)
- Ophthalmic primary underlying condition (autoimmune disease, chemical injury, mechanical injury, other)
- Previously/currently treated for elevated IOP or glaucoma (no, yes)

Summary statistics will be tabulated for

- the time since the onset of the ophthalmic primary underlying condition and the date of surgery (in years)
- the axial length (in mm)

7.3. External Eye Photography

External eye photographies performed at the screening examination will be displayed by patient in a patient data listing. In addition, the reason will be listed when no photography was performed.

7.4. Anterior Eye Segment Assessments

Findings of the slit-lamp biomicroscopy will be summarized overall ('any finding') and by segment (lids, conjunctiva, cornea, anterior chamber, iris, pupil, lens, aqueous humor, other) and will include the number and percentage of patients with at least one finding reported. A summary table will be

Statistical Analysis Plan

Version 1.0 [Final], 09-Jan-2018

generated on a patient level: Patients are counted only once for each segment when they have more than one finding within the segment of the anterior eye.

In addition, clinically significant findings will be summarized overall ('any finding') and by segment and will include the number and percentage of patients with at least one clinically significant finding reported. A summary table will be generated on a patient level: Patients are counted only once for each segment when they have more than one clinically significant finding within the segment of the anterior eye.

Further description of the anterior segment findings including severity will be presented in corresponding patient data listings only.

Measurements regarding the cup disc ratio, central retinal thickness and white-to-white diameters will be listed in a patient data listing.

7.5. Posterior Eye Segment Assessments

Findings will be summarized overall ('any finding') and by segment (fundus, macula, retina, vitreous body, other) and will include the number and percentage of patients with at least one finding reported. A summary table will be generated on a patient level: Patients are counted only once for each segment when they have more than one finding within the segment of the posterior eye.

In addition, clinically significant findings will be summarized overall ('any finding') and by segment and will include the number and percentage of patients with at least one clinically significant finding reported. A summary table will be generated on a patient level: Patients are counted only once for each segment when they have more than one clinically significant finding within the segment of the posterior eye.

Further description of the posterior segment findings including severity will be presented in corresponding patient data listings only.

7.6. IOP measurements

Measurements of the intra-ocular pressure (IOP) are performed at the beginning and at the end of the screening visit using Goldmann Applanation Tonometry and/ or pneumotonometry.

Summary statistics will be tabulated for IOP measurements (in mmHg) by measurement procedure (Goldmann Applanation Tonometry, pneumotonometry) and time point (beginning, end of the visit).

Further details (time of measurements) will be presented in a corresponding patient data listing.

7.7. Medical History and Concomitant Diseases

Medical history are all diagnoses/procedures where the stop date is on the date of the surgery (Day 0) or before, and *concomitant diseases* are all diagnoses/procedures with either a ticked 'Ongoing?' box or a stop date after the date of surgery (Day 0). If start date and stop date are identical and the date of surgery, the disease will only be evaluated as concomitant disease.

Medical history and concomitant diseases are coded according to the MedDRA terminology (version 20.0).

Statistical Analysis Plan

Version 1.0 [Final], 09-Jan-2018

Medical history findings and concomitant diseases will be summarized separately by System Organ Class and Preferred Term and will include the number and percentage of patients with at least one disease reported. Summary tables will be generated on a patient level: Patients are counted only once for each preferred term when they have more than one disease with the same preferred term. Patients with more than one disease within a SOC will be counted for each corresponding preferred term within the SOC, but are counted only once for the SOC. All tabulations will be sorted alphabetically by SOC and by frequency of preferred terms within each SOC.

Corresponding tables will be presented for the medical history findings and concomitant diseases regarding the study eye.

Specific previous/concomitant disease findings will be presented in a corresponding patient data listing.

7.8. Prior and Concomitant Medications and Non-drug Therapies

Prior medications or prior non-drug therapies are all medications or non-drug therapies where the stop date is before the date of surgery (Day 0). *Concomitant medications or concomitant non-drug therapies* are all medications or non-drug therapies with either a ticked 'Ongoing?' box or a stop date on or after the date of surgery (Day 0). If start date and stop date are identical and the date of surgery, the medication or non-drug therapy will only be evaluated as concomitant medication or concomitant non-drug therapy.

Recorded medications are coded according to WHO-DDE (version 2012/Q4). The allocation of reported terms to higher-level classifications is made using the preferred ATC code.

Prior and concomitant medications will be summarized separately using Level 2 (3-digit) and Level 3 (4-digit) of the ATC code. Summary tables will be generated on a patient basis: Patients are counted only once for each ATC class when they have more than one medication within the same ATC class. Patients with more than one medication within a level 2 ATC class will be counted for each corresponding level 3 term, but only once for the level 2 class. The number and percentage of patients with at least one medication reported will also be displayed. All tabulations will be sorted alphabetically by level 2 ATC decode and by frequency of level 3 decodes within level 2 class.

Specific details of prior or concomitant medication findings (e.g. dose, route and frequency of administration) will be presented in corresponding patient data listings only.

Note: Reported medications or non-drug therapies which a start date after the date of study termination will only be presented and flagged in the patient data listing but not tabulated in summary tables.

7.9. Other Baseline Characteristics

Regarding female patients, childbearing potential and the result of a urine pregnancy test before investigational device implantation will be listed in a patient data listing.

8. Clinical Investigation Treatments**8.1. Findings Associated with Surgery**

The following descriptive statistics will be presented for each analysis population:

Statistical Analysis Plan

Version 1.0 [Final], 09-Jan-2018

- A frequency table regarding intraocular lens (IOL): patient pseudophakic (yes, no), IOL location (posterior, other location), disposition of IOL (removed, remained in eye)
- A frequency table regarding iridectomy: iridectomy performed (yes, no), method (manual, laser), location
- A frequency table regarding glaucoma drainage device (GDD): GDD in situ at start of surgery (yes, no), GDD left in place (yes, no), GDD implanted during surgery (yes, no), GDD now (yes, no), location of GDD (superior 12 o'clock, nasal, inferior 6 o'clock, temporal)
- A frequency table regarding keratoprosthesis device: implanted (yes, no)

8.2. Investigational Device

The details for the implantation of the ARGOS-IO will be tabulated in a frequency table for

- Implantation performed (yes, no)
- Size of the sensor (11.3 mm, 11.7 mm, 12.1 mm)
- Placement of the ARGOS-IO sensor: sulcus support adequate (yes, no, not assessed), fixation of the sensor
- Orientation of application specific integrated circuit (ASIC) (superior 12 o'clock, nasal, inferior 6 o'clock, temporal)

In addition, the number and percentage of patients with intraoperative complications will be presented in a table. The specification of the intraoperative complications and any difficulties with the placement of the ARGOS-IO sensor will be presented in the corresponding patient data listing.

Further information including data regarding keratoprosthesis and discharge date will be given in patient data listings.

8.3. Rescue Medication

N/A

9. Performance Analyses

All statistical tables will show the results for all patients of the PPS (primary analyses) and the SFS.

Concerning IOP, a summary of all manometry and ARGOS-IO system measurements will be displayed in a table by visit (Week 4, 16, 28, 52 visit): For each patient the mean value of the ARGOS-IO system measurements (mean within subject value) at the visit will be derived and the difference to the manometry value calculated.

The difference between manometry and ARGOS-IOP measurements will be displayed over time in a mean value plot.

Pairs of measurement will only be used when there was no more than 2 minutes difference between manometry and ARGOS-IO system measurements.

All measurement values including the mean within subject ARGOS IOP value will be displayed in a patient data listing. In addition, the time points of measurements and the difference between the time points will be presented in the listing.

9.1. Primary Performance Endpoint

Primary performance endpoint is the level of agreement between IOP measurements made using manometry and the ARGOS-IO system over the first 12 months following implantation of the IMD.

A Bland-Altman analysis will be done for a point estimation of the level of agreement between the two IOP measurement methods with repeated observations. It is assumed that the true IOP value varies over time for each patient.

Concerning ARGOS-IO, the average of the (three) measurements during surgical manometry will be taken.

All complete measurement pairs (manometry value, average of the ARGOS-IO values during surgical manometry) will be used per patient, to calculate the mean within subject difference between the methods. Pairs of measurement will only be used when there was no more than 2 minutes difference between both measurements.

The average over the mean within subject differences (Δ) is an estimate for the bias between the two IOP measurement methods. The lower and the upper level of agreement will be estimated as

$$\text{LoA}_{\text{low}} = \Delta - z_{\beta/2} * s$$

$$\text{LoA}_{\text{upp}} = \Delta + z_{\beta/2} * s$$

($z_{\beta/2}$ is the upper $\beta/2$ quantile of the standard normal distribution ($=1.96$), s is an estimate for the variation of the differences which comprises both between and within individual components, see Zou, section 2.1.1)

95% confidence interval estimation for the lower limit of agreement (LoA_{low}) and for the upper limit of agreement (LoA_{upp}) will be obtained using the MOVER method, see Zou, section 2.2.2.

9.2. Secondary Performance Endpoint: Level of Agreement at Specific Visits

Secondary performance endpoint is the level of agreement between IOP measurements made using surgical manometry and the ARGOS-IO system at visits 4, 16, 28 and 52 weeks following implantation.

For each of the visits mentioned above a Bland-Altman analysis will be done to assess the level of agreement between the two IOP measurement methods. Concerning ARGOS-IO, the average of the (three) measurements during surgical manometry will be taken.

For each of the visits mentioned above, the mean of the within subject differences and 95% limits of agreement between the two methods will be calculated. Pairs of measurement will only be used when there was no more than 2 minutes difference between both measurements.

For each of the visits mentioned above, the within subject differences will be plotted against the within subject means (Bland-Altman plot).

9.3. Secondary Performance Endpoint: Incidence of Device Deficiencies

Statistical Analysis Plan

Version 1.0 [Final], 09-Jan-2018

Secondary performance endpoint is the incidence of device deficiencies in the first 4, 16, 28 and 52 weeks following implantation.

A summary table on device deficiencies will be generated displaying the number and percentage of patients with any device deficiency in the first 4, 16, 28 and 52 weeks following implantation. In addition, the number and percentage of patients with a device deficiency regarding the ARGOS-IO implant, the Mesograph reader, the multiline connector or other will be presented in the table for each of the periods mentioned above.

All device deficiencies and associated collected information will be presented in a corresponding patient data listing.

9.4. Secondary Performance Endpoint: User Acceptance of the Implantation Procedure

Data are not available in the database for the Investigator Implantation Procedure Questionnaire scheduled for the evaluation of the user acceptance.

9.5. Secondary Performance Endpoint: User Acceptance of the ARGOS-IO System

Data are not available in the database for the Investigator Acceptance Questionnaire scheduled for the evaluation of the user acceptance.

9.6. Unplanned Analysis

Summary statistics will be presented in a table by visit (Week 4, 16, 28, 52 visit) and time point (measurement 1 - prior to manometry, measurement 2 - during manometry, measurement 3 - following manometry) for the within subject mean IOP values. Concerning each patient and time point, the maximal difference between the IOP values will be derived and summarized in the table.

Concerning each post-surgery visit, the within subject mean IOP value will be derived for measurement 1 (at the beginning of the visit). Summary statistics will be tabulated for the within subject mean IOP value by the result of finger palpation assessment of IOP (soft/ hypotonic, borderline, normal, hypertonic). Furthermore, within subject mean IOP value and finger palpation assessment will be presented per patient in a scatter plot.

10. Safety Analyses

All safety parameters will be evaluated on the SFS. Only descriptive statistics will apply.

10.1. Primary Safety Endpoint: Occurrence of Serious Adverse Device Events (SADE)

The number and percentage of patients experiencing a device related SAE at any time during the first 12 months following implantation surgery will be presented in a table. In addition, a 95% confidence interval will be calculated for the percentage of patients with SADE as specified above.

For the purpose of this analysis, a device-related SAE is defined as any serious adverse event that is considered by the Investigator to have a possible, probable or definite relationship to the device.

10.2. Secondary Safety Endpoints: Incidence and Description of Adverse Events

All adverse events (AEs) including all adverse device effects (ADEs) as recorded in the CRF module 'Adverse Events' will be analyzed.

Initially, an overview will be generated tabulating the number and proportion of patients (and the total number of events) with

- AEs
- Adverse device effects (all adverse events that are considered by the Investigator to have a possible, probable or definite relationship to the medical device)
- AEs related to procedure (all adverse events that are considered by the Investigator to have a possible, probable or definite relationship to the procedure)
- AEs leading to withdrawal of patient
- serious AEs

All adverse events at any time during the first 12 months following implantation surgery will be considered. In addition, 95% confidence intervals will be presented for the percentage of patients with AE(s) considered as specified above.

Corresponding overview tables will be given describing the number and proportion of patients with adverse events as specified above at any time during the first 4 weeks, during the first 16 weeks, and during the first 28 weeks following implantation of the IMD, respectively. In addition, 95% confidence intervals will be presented for the percentage of patients with AE(s) considered as specified above.

All adverse events with onset date during the period will be considered.

- AEs with incomplete onset date will be regarded with an onset date completed by '01' for the day (when the month and the year of the onset date are known)
- AEs with an unknown onset date will be regarded with an onset date identical to the date of awareness of the AE

Note that AEs will be counted for each period since onset. Reported frequencies are cumulative over the time for this reason.

Adverse events are coded according to the MedDRA terminology. The following summaries will be provided for adverse events broken down by System Organ Class (SOC) and Preferred Term within SOC:

- All AEs
- All AEs by severity (categories: mild, moderate, severe)
- All AEs by causal relationship to IMD (categories: none, unlikely, possible, probable or definite)
- All adverse device effects (all adverse events that are considered by the Investigator to have a possible, probable or definite causal relationship to the device)
- All AEs related to procedure (all adverse events that are considered by the Investigator to have a possible, probable or definite causal relationship to the procedure)
- All adverse device effects by severity
- All serious AEs
- All serious adverse device effects

Statistical Analysis Plan

Version 1.0 [Final], 09-Jan-2018

These summaries will generally provide the number and percentage of patients with AEs (and the total number of events) within each preferred term and within each SOC. Patients are counted only once for each preferred term when they have more than one AE with the same preferred term. Patients with more than one AE within a SOC will be counted for each corresponding preferred term within the SOC, but are counted only once for the SOC. The number of patients with at least one AE and the total number of events will also be displayed.

These summaries will be provided for adverse events at any time during the first 4 weeks, during the first 16 weeks, during the first 28 weeks and at any time during the first 12 months following implantation surgery, broken down by System Organ Class (SOC) and Preferred Term within SOC.

All tabulations will be sorted alphabetically by SOC and by frequency of preferred terms within each SOC.

A glossary of adverse events will be presented showing how investigator reported terms were actually coded to preferred terms and body systems.

All adverse events and associated collected information will be presented by patient in a corresponding patient data listing.

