3.3.3.5 AEs/ADEs/SAEs/SADEs

All AEs/ADEs/SAEs/SADEs were recorded starting with the implantation of the ARGOS-IO pressure sensor.

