4.4. Definition of Derived Variables

In case a proportion for a specified criterion is computed, all patients meeting the criterion will be divided by the number of all patients within a population.

In this study, Baseline is the value recorded at Screening visit. If no value at Screening visit is available, the pre-surgical value will be used as Baseline assessment (if applicable).

Changes from Baseline (if applicable) will be computed as follows:

- Absolute change (original unit): post-Baseline value – Baseline value
- Relative change (%): $100 \times (\text{post-Baseline value} - \text{Baseline value}) / \text{Baseline value}$
If the Baseline value is 0, no relative change will be computed.

Adverse events should be documented from the point of surgery until the patient is discharged from the clinical investigation..

A flag variable will be defined indicating for each adverse event the period of the onset:

- up to 4 weeks (Day 0 – Day 28) after surgery
- after 4 weeks up to 16 weeks (Day 29 – Day 112)
- after 16 weeks up to 28 weeks (Day 113 – Day 196)
- after 28 weeks up to 12 months (Day 197 – max(Day 365, Day of study termination))

Statistical Analysis Plan

Version 1.0 [Final], 09-Jan-2018

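### SAP 10.2 completes a missing AE onset day with '01' and sets no floor at surgery, so a surgery-month AE can be dated before surgery, outside every SAP 4.4 onset period

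*SAP*

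**What the plan says.** SAP 10.2 has two rules for dating an AE with a defective onset date. If month and year are known, "AEs with incomplete onset date will be regarded with an onset date completed by '01' for the day". If nothing is known, "AEs with an unknown onset date will be regarded with an onset date identical to the date of awareness of the AE". Neither rule mentions the date of surgery.

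The dates then decide where an event is counted:

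- SAP 10.2, period tables: "All adverse events with onset date during the period will be considered". A note adds: "Note that AEs will be counted for each period since onset". Frequencies are therefore cumulative over 4, 16 and 28 weeks and 12 months.
- SAP 10.2, 12-month overview: "All adverse events at any time during the first 12 months following implantation surgery will be considered". The section opens by saying that all AEs recorded in the CRF's adverse event module will be analysed.
- SAP 4.4 defines a flag that gives each AE a period of onset. The earliest is "up to 4 weeks (Day 0 – Day 28) after surgery"; the others start at Days 29, 113 and 197.
- SAP 10.1 counts patients with a device-related SAE "at any time during the first 12 months following implantation surgery" and gives no dating rule of its own.

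On collection, SAP 4.4 documents AEs from surgery onwards, and Protocol 3.3.3.5 states: "All AEs/ADEs/SAEs/SADEs were recorded starting with the implantation of the ARGOS-IO pressure sensor".

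**The concern.** Every recorded AE has a true onset on or after Day 0, so a completed date before surgery is always wrong. The '01' rule produces such a date for any surgery-month AE with a missing day, except where surgery was on the 1st.

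SAP 4.4 has no period for a negative study day, so the flag cannot be assigned as defined. For the tables, the text leaves the programmer two options. If onset is tested against both ends of the window, the event is in none of the four tables, because all four windows start at surgery. If only the upper end is tested, the event stays in all four. The first option contradicts the opening sentence of 10.2; the second relies on something the SAP does not say.

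The serious adverse device effect summaries are among the outputs that 10.2 lists for these same periods (Table 14.3.2.2), so they are exposed on the same terms. Whether the rule also dates events for the 10.1 primary count (Table 14.3.1.1) is an inference, because 10.1 is silent. With 13 patients in the safety set, one patient more or less is visible in a rate.

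**Working it through.** The plan has no figure of its own to reproduce here. The check is date arithmetic.

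**Inputs.** Completion rule: SAP 10.2. Periods Day 0–28, 29–112, 113–196 and 197 onwards: SAP 4.4. Start of AE recording: SAP 4.4 and Protocol 3.3.3.5. Assumption: surgery dates and onset days are uniform.

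**Formula.** Completed study day = (1st of the onset month) − (date of surgery).

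**Single case.** With surgery on 15 June and onset in June, day missing: 1 June − 15 June = Day −14. No SAP 4.4 period contains it.

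**Which surgery dates are exposed.** In a non-leap year, 365 − 12 = 353 surgery dates are not the 1st of a month; 353/365 = 96.7%. For these, a day-missing surgery-month AE gets a completed day between −30 and −1.

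**Which onsets are exposed.** The count runs over 730 consecutive surgery dates (two calendar years) and every true onset day in the range, with the onset day removed:

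| True onset | Combinations | Dated before surgery |
|---|---|---|
| Days 0–7 | 730 × 8 = 5,840 | 4,983 (85.3%) |
| Days 0–28 | 730 × 29 = 21,170 | 10,759 (50.8%) |
| Days 29–112 | 730 × 84 = 61,320 | 14 (0.02%) |

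These are shares of AEs that lack a day, not shares of all AEs.

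**With a floor.** Completed onset = max(1st of month, date of surgery). Under the present rule with a literal Day 0 bound, 21,170 − 10,759 = 10,411 (49.2%) of the Day 0–28 combinations fall in the first period. With the floor, all 21,170 do. The 14 later combinations are surgery on the 2nd and onset on the 31st of a 31-day month (Day 29): 7 such months × 2 years. The floor puts them in the 4-week table. The general backward shift of the '01' rule across later boundaries is not changed: about 17.5% of day-missing Day 29–112 onsets go to the first period with or without the floor.

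**What one patient would mean.** This shows scale only and is not an estimate. Table 11 reports 4 of 13 patients with a device effect at 12 months: 30.8%, Clopper-Pearson 95% CI 9.1 to 61.4. Three of 13 would be 23.1%, CI 5.0 to 53.8.

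**Signs of loss in the report.** Section 4.8.1 gives 168 AEs overall and 168 at 12 months. The causality split is 92 + 61 + 15 = 168. The system organ class event counts in Table 9 sum to 167, or 168 if the blank Ear and Labyrinth row is one event. All three agree, although they may share one source.

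**The case against.** The opening of 10.2 says that all recorded AEs will be analysed, and SAP 4.4 intends a period for each AE. Since recording starts at surgery, the Day 0 bound was hardly meant as a filter. Read together, these passages favour keeping the event. Partial dates should also be rare in this window: visits fall on Days 1, 5, 10, 15 and Week 4, and Protocol 3.5 has data management query missing, out-of-range or questionable data, with all queries answered before lock. Every AE also appears in the patient listings, and the analysis is descriptive.

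Most of this stands, and it limits the size of the point. It does not remove it. The intention to keep every AE does not say what date or flag a Day −14 event should carry. The SAP expects some partial dates to survive, since it has a rule for them. Double programming (SAP 5.1) does not help if both programmers apply the same rule. SAP 5.3 says missing data are not imputed and supplies no floor.

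A reader might go further and infer that early AEs were lost from the reported tables, or that the primary safety count is too low. The documents support neither. They show no AE with a missing onset day, and the totals agree. Multiplying the reported 4-week counts by an assumed partial-date rate would not estimate a loss either: the rate has no basis in the documents, and on the literal reading lost events would already be absent from those counts. The pages with Table 12 (serious device effects by time) are not available here, so the number of early ones is unknown.

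**Conclusion.** The point holds as a minor defect in a stated rule. SAP 10.2 gives an impossible onset date to a surgery-month AE with a missing day unless surgery was on the 1st, and SAP 4.4 has no period for that date. Under uniform surgery and onset days, this affects about 51% of day-missing Day 0–28 onsets.

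Exclusion from the tables follows only if the Day 0 bound is applied literally, against the opening sentence of 10.2; with upper cut-offs alone, none is lost. The link to the serious adverse device effect summaries in 10.2 is in the text. The link to the 10.1 primary count is inferred. The number of AEs with a missing day is not given, so no number of lost AEs or serious device effects should be stated, and nothing in the report suggests that any were lost.

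**What to change.** In SAP 10.2, set an incomplete onset date to the later of the 1st of the month and the date of surgery. In SAP 10.1, state that the same dating applies to the count of patients with a serious device-related event. Check Listings 16.2.7.1 and 16.2.7.2 for partial dates in a surgery month, and rerun the AE tables only if one is found; the statistical outputs are already final (Version 2.0, 21FEB2018).

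The cost is one clause, one sentence and a check of two listings. The downside is that a floored event may be placed too early, by at most 29 days. In rare cases (14 of 61,320 combinations) this puts a Day 29 onset in the 4-week table. The 12-month count is not distorted by this.
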